## 6.7 Diet, Sexual Activity, and Other Considerations

### 6.7.1 Diet

Subjects should maintain a normal diet unless modifications are required to manage an AE such as diarrhea, nausea or vomiting.

### 6.7.2 Sexual Activity

#### 6.7.2.1 *Contraception*

Pembrolizumab may have adverse effects on a fetus in utero. Furthermore, it is not known if pembrolizumab has transient adverse effects on the composition of sperm.

For this trial, male subjects will be considered to be of non-reproductive potential if they have azoospermia (whether due to having had a vasectomy or due to an underlying medical condition).

Female subjects will be considered of non-reproductive potential if they are either:

1. Postmenopausal (defined as at least 12 months with no menses without an alternative medical cause; in women < 45 years of age a high follicle stimulating hormone (FSH) level in the postmenopausal range may be used to confirm a post-menopausal state in women not using hormonal contraception or hormonal replacement therapy. In the absence of 12 months of amenorrhea, a single FSH measurement is insufficient.);

**OR**

2. Have had a hysterectomy and/or bilateral oophorectomy, bilateral salpingectomy or bilateral tubal ligation/occlusion, at least 6 weeks prior to screening;

**OR**

3. Has a congenital or acquired condition that prevents childbearing.

Female and male subjects of reproductive potential must agree to avoid becoming pregnant or impregnating a partner, respectively, while receiving study drug and for 120 days after the last dose of study drug by complying with one of the following:

Practice abstinence† from heterosexual activity

**OR**

Use (or have their partner use) acceptable contraception during heterosexual activity.

Acceptable methods of contraception are‡:

Single method (one of the following is acceptable):

CASE 1516

Protocol Amendment 7

06/06/2019

- Intrauterine device (IUD)
- Vasectomy of a female subject's male partner
- Contraceptive rod implanted into the skin

Combination method (requires use of two of the following):

- Diaphragm with spermicide (cannot be used in conjunction with cervical cap/spermicide)
- Cervical cap with spermicide (nulliparous women only)
- Contraceptive sponge (nulliparous women only)
- Male condom or female condom (cannot be used together)
- Hormonal contraceptive: oral contraceptive pill (estrogen/progestin pill or progestin-only pill), contraceptive skin patch, vaginal contraceptive ring, or subcutaneous contraceptive injection

*†Abstinence (relative to heterosexual activity) can be used as the sole method of contraception if it is consistently employed as the subject's preferred and usual lifestyle and if considered acceptable by local regulatory agencies and ERCs/IRBs. Periodic abstinence (e.g., calendar, ovulation, sympto-thermal, post-ovulation methods, etc.) and withdrawal are not acceptable methods of contraception.*

*‡If a contraceptive method listed above is restricted by local regulations/guidelines, then it does not qualify as an acceptable method of contraception for subjects participating at sites in this country/region.*

Subjects should be informed that taking the study medication may involve unknown risks to the fetus (unborn baby) if pregnancy were to occur during the study. In order to participate in the study subjects of childbearing potential must adhere to the contraception requirement (described above) from the day of study medication initiation (or 14 days prior to the initiation of study medication for oral contraception) throughout the study period up to 120 days after the last dose of trial therapy. If there is any question that a subject of childbearing potential will not reliably comply with the requirements for contraception, that subject should not be entered into the study.

#### **6.7.2.2 Use in Pregnancy**

If a subject inadvertently becomes pregnant while on treatment with pembrolizumab, the subject will immediately be removed from the study. The site will contact the subject at least monthly and document the subject's status until the pregnancy has been completed or terminated. The outcome of the pregnancy will be reported to the Sponsor and to Merck without delay and within 24 hours to the Sponsor and within 2 working days to Merck if the outcome is a serious adverse experience (e.g., death, abortion, congenital anomaly, or other disabling or life-threatening complication to the mother or newborn).

The study investigator will make every effort to obtain permission to follow the outcome of the pregnancy and report the condition of the fetus or newborn to the Sponsor. If a male subject impregnates his female partner the study personnel at the site must be informed immediately and the pregnancy reported to the Sponsor and to Merck and followed as described above and in Section 7.4.

#### **6.7.2.3 Use in Nursing Women**

It is unknown whether pembrolizumab is excreted in human milk. Since many drugs are excreted in human milk, and because of the potential for serious adverse reactions in the nursing infant, subjects who are breast-feeding are not eligible for enrollment.

### **6.8 Trial Compliance (Medication/Diet/Sexual Activity/Other)**

Interruptions from the protocol specified treatment plan for > 3 weeks require consultation between the investigator and the Sponsor and written documentation of the collaborative decision on subject management.

The total volume of trial treatment infused will be compared to the total volume prepared to determine compliance with each dose administered. The instructions for preparing and administering pembrolizumab will be provided in the Pharmacy Manual. Standard of care therapy will be prepared and administered as per the approved product label

### **6.9 Withdrawal/Discontinuation**

Subjects may withdraw consent at any time for any reason or be dropped from the trial at the discretion of the investigator should any untoward effect occur. In addition, a subject may be withdrawn by the investigator or the Sponsor if enrollment into the trial is inappropriate, the trial plan is violated, or for administrative and/or other safety reasons. When a subject discontinues/withdraws prior to trial completion, all applicable activities scheduled for the final trial visit should be performed at the time of discontinuation. Any adverse events which are present at the time of discontinuation/withdrawal should be followed in accordance with the safety requirements outlined in Section 7.2 - Assessing and Recording Adverse Events. Subjects who a) attain a CR or b) complete 24 weeks of treatment with pembrolizumab may discontinue treatment with the option of restarting treatment if they meet the criteria specified in Section 6.9.1. After discontinuing treatment following assessment of CR, these subjects should return to the site for a Safety Follow-up Visit (described in Section 6.3.1) and then proceed to the Follow-Up Period of the study (described in Section 6.3.1.1).

A subject must be discontinued from the trial for any of the following reasons:

- The subject or legal representative (such as a parent or legal guardian) withdraws consent.
- Confirmed radiographic disease progression

*Note: A subject may be granted an exception to continue on treatment with confirmed radiographic progression if clinically stable or clinically improved.*

CASE 1516

Protocol Amendment 7

06/06/2019

- Unacceptable adverse experiences as described in Section Intercurrent illness that prevents further administration of treatment
- Investigator's decision to withdraw the subject
- The subject has a confirmed positive serum pregnancy test
- Noncompliance with trial treatment or procedure requirements
- The subject is lost to follow-up
- Administrative reasons

The End of Treatment and Follow-up visit procedures are listed in Section 6.2.2 (Treatment Regimen Overview). After the end of study treatment, each subject will be followed for 30 days for adverse event monitoring. Subjects who discontinue study treatment for reasons other than progressive disease will have post-treatment follow-up visits for disease status every 9 weeks +/- 14 days until disease progression, initiating a non-study cancer treatment, withdrawing consent, or becoming lost to follow-up. Additionally, subjects who continue to receive pembrolizumab as standard of care will be followed for disease status every 9 weeks +/- 14 days until disease progression, initiating a non-study cancer treatment, withdrawing consent, or becoming lost to follow-up. After documented disease progression or initiation of a non-study cancer treatment, each subject will be followed by telephone for overall survival until death, withdrawal of consent, or the end of the study, whichever occurs first.

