##### 3.1.1 Tumor Imaging and Assessment of Disease

The initial tumor imaging will be performed within 30 days prior to the first dose of trial treatment. CT scans are the required modality for measurable disease unless a subject has a clinical condition e.g. severe contrast allergy, or the lesions are significantly better visualized through the use of an MRI. The same imaging technique must be used for a subject throughout the study. Scans performed as part of routine clinical management are acceptable for use as the screening scan if they are of diagnostic quality and performed within 30 days prior to the first dose of trial treatment. Repeat imaging would be performed after every 2 cycles of therapy for the remainder of the on-study treatment period or more frequently if clinically indicated. CT timing should follow calendar days and should not be adjusted for delays in cycle starts or extension of pembrolizumab cycle frequencies. This protocol recommends that patients receiving pembrolizumab as standard of care after EOT will have CT scans every 9 weeks +/- 14 days until the subject experiences confirmed disease progression or starts a new antineoplastic therapy.

Subjects who discontinue trial treatment for reasons other than disease progression should also receive tumor imaging every 9 weeks +/- 14 days until the subject experiences confirmed disease progression or starts a new antineoplastic therapy.

Disease progression for trial eligibility will be according to RECIST 1.1 criteria. Local reading (investigator assessment with site radiology reading) will be used to determine eligibility and for subject management. De-identified imaging will also be obtained from all participating sites for

imaging correlative studies to be done by collaborators at Case Western Reserve University Biomedical Engineering group.

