### **3.4 Expected Duration of Treatment and Subject Participation**

Subjects will complete 8 cycles (28 weeks) of on study treatment. Before they begin study treatment they will receive SFRT to one or more target lesions. If participants experience complete response while on study treatment they will stop treatment with pembrolizumab. If they experience recurrence after this time they have the option of re-starting treatment on trial as long as all eligibility requirements are still met.

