#### **6.3.1.1 *Survival Follow-Up***

Subjects will be followed every 12 weeks +/- 14 days post study for survival status and record of anti-cancer treatments for up to 5 years in follow-up until death, withdrawal of consent, or the end of the study, whichever occurs first. If the subject has any anti-cancer treatments subsequent to study completion at any time during that five year follow-up period, their subsequent treatment would be recorded. This will be done by review of patients' medical records, communication with patients treating physicians, review of public obituary records or contact of patients by telephone.

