**Table 3 - STUDY SCHEMA**

Trial Period:	Screening Phase	Treatment Cycles a								End of Treatment	Post Study Treatment		
		1	2	3	4	5	6	7	8		Safety Follow-up	SOC Treatment Period (if applicable)	Survival Follow Up b
Treatment Cycle/Title:	Main Study Screening Visit									Cycle 8 or off study due to progression/toxicity			
Scheduling Window (Days):	-28 to -1		± 7	± 7	± 7	± 7	± 7	± 7	± 7	At time of Discontinuation	30 days (± 7) post discontinuation	Per SOC guidelines	Every 12 weeks (± 14 days) post discontinuation
Administrative Procedures													
Informed Consent/ Inclusion/Exclusion Criteria	X												
Prior and Concomitant Medication Review	X	X	X	X	X	X	X	X	X	X	X		
Pembrolizumab		X	X	X	X	X	X	X	X			X	
SFRT		X											
Survival Status/ Post-study anticancer therapy status											X	X	X
Clinical Procedures/Assessment													
Review Adverse Events	X	X	X	X	X	X	X	X	X	X	X		
Full Physical Examination	X e												
Directed Physical Examination	X	X	X	X	X	X	X	X	X	X	X		
ECOG Performance Status	X	X	X	X	X	X	X	X	X				
Local Laboratory Procedures/Assessments													
Pregnancy Test – Urine or Serum β-HCG	X i												
CBC with Differential	X f		X	X	X	X	X	X	X				
Comprehensive Metabolic Panel	X f		X	X	X	X	X	X	X				
T3, FT4 and TSH	X f			X		X		X					
Efficacy Measurements													
Tumor Imaging c	X g			X		X		X				X h	
Tumor Biopsies/Archival Tissue Collection/Correlative Studies Blood													
Archival or Newly Obtained Tissue Collection	X d			X d									

CASE 1516

Protocol Amendment 7

06/06/2019

Peripheral Blood/Flow	X			X		X			X			
Serum	X			X		X			X			
PBMC/IRC	X		X	X	X	X	X	X	X			

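### Section 6.9 sends patients who stop after complete response to survival-only follow-up, and Table 3 shows no scan for anyone off treatment without progression; both conflict with the 9-weekly assessments in Sections 3.1.1 and 6.9

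*Combined protocol and SAP*

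**What the plan says.** Two sets of passages describe what happens to a patient who leaves treatment without progression.

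**Disease follow-up continues.** Section 3.1.1: "Subjects who discontinue trial treatment for reasons other than disease progression should also receive tumor imaging every 9 weeks +/- 14 days", until confirmed progression or a new antineoplastic therapy. A later paragraph of Section 6.9 agrees in substance: "Subjects who discontinue study treatment for reasons other than progressive disease will have post-treatment follow-up visits for disease status every 9 weeks". That paragraph starts telephone follow-up for survival only once progression is documented or a non-study cancer treatment begins.

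**Survival follow-up only.** An earlier paragraph of Section 6.9 says that patients who stop after CR attend the Safety Follow-up Visit and "then proceed to the Follow-Up Period of the study (described in Section 6.3.1.1". Section 6.3.1.1 reads: "Subjects will be followed every 12 weeks +/- 14 days post study for survival status and record of anti-cancer treatments". Its methods are chart review, contact with treating physicians, and "review of public obituary records or contact of patients by telephone". It contains no disease assessment.

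**The schedule table.** Section 6.2.2 describes the study schema as the complete list of procedures, including those in follow-up, and Section 6.9 refers to 6.2.2 for the end-of-treatment and follow-up visits. In Table 3 the tumor imaging row is marked at screening, cycles 3, 5 and 7, and under "SOC Treatment Period (if applicable". Footnote h confines that last mark to patients still receiving standard-of-care pembrolizumab. Footnote b postpones survival follow-up until progression or new therapy, again only for those patients.

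**Whether CR patients stop.** Section 3.4: "If participants experience complete response while on study treatment they will stop treatment with pembrolizumab". Section 6.9 makes stopping at CR optional.

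**The concern.** The CR sentence in 6.9 is the only one that names CR stoppers, so a site could reasonably take it as the specific rule that displaces the general one. Table 3 would appear to confirm that reading, because it offers no column with a scan for someone off treatment and progression-free.

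The secondary endpoints need those scans. Section 2.2.2 defines PFS by documented, confirmed progression and lists durable response at 6 and 12 months. Section 8 summarizes PFS and response duration by Kaplan-Meier. Section 3.4 also offers a restart on trial after recurrence following CR, and survival-only follow-up has no scheduled means of detecting recurrence. Scans not done at the time cannot be recovered at analysis.

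**Working it through.** No design figure is at issue, so there is no stated number to reproduce. The check is a comparison of passages followed by scan-calendar arithmetic.

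**1. Passages side by side**

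| Patient off treatment, no progression | 3.1.1 | 6.9, later paragraph | 6.9, CR sentence (to 6.3.1.1) | Table 3 and footnotes |
|---|---|---|---|---|
| Stopped after CR | Imaging every 9 weeks ± 14 days | Disease-status visit every 9 weeks ± 14 days | Survival contact every 12 weeks | No scan marked |
| Stopped for toxicity or another reason | Imaging every 9 weeks ± 14 days | Disease-status visit every 9 weeks ± 14 days | Not addressed | No scan marked |

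For CR stoppers, two instructions in the text conflict and the table sides with the survival-only route. For other stoppers the text is consistent, and the defect is only the missing table entry. Of the two passages that keep patients in disease follow-up, only 3.1.1 names imaging.

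**2. Scan calendar**

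Inputs: 3-week cycles (Table 2), imaging before cycles 3, 5 and 7 (Table 3), and 9-weekly imaging after stopping (3.1.1). Cycle c starts at week 3 × (c − 1), so the on-study scans in Table 3 fall at weeks 6, 12 and 18. The documents do not say when the durability clock starts. I assume first pembrolizumab, with 6 and 12 months taken as weeks 26 and 52.

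| Stops after scan at | Unscanned before week 26, survival-only route | Unscanned before week 52, survival-only route | Scans under 3.1.1 (weeks) |
|---|---|---|---|
| Week 6 | 26 − 6 = 20 weeks | 52 − 6 = 46 weeks | 15, 24, 33, 42, 51, 60 |
| Week 12 | 26 − 12 = 14 weeks | 52 − 12 = 40 weeks | 21, 30, 39, 48, 57 |
| Week 18 | 26 − 18 = 8 weeks | 52 − 18 = 34 weeks | 27, 36, 45, 54, 63 |

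Under 3.1.1 both landmarks are bracketed by scans in every row (in the last row, week 26 lies between the week 18 scan and week 27). On the survival-only route neither landmark is reached by a scheduled scan. If the clock starts at first response instead, the landmarks move at least 6 weeks later, because the first on-study scan is at week 6. The gaps then lengthen by at least that much.

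**3. How many patients**

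The documents give no CR rate. Under assumed rates of 1%, 2%, 5% and 10%, the expected number of CRs in 48 patients is 48 × 0.01 = 0.5, 48 × 0.02 = 1.0, 48 × 0.05 = 2.4 and 48 × 0.10 = 4.8. These illustrate the order of magnitude and are not estimates. Not every CR need lead to a stop, given the difference between 3.4 and 6.9.

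**The case against.** The strongest answer is that the protocol already requires these assessments twice. Sections 3.1.1 and 6.9 both cover everyone who stops without progression, and the 6.9 rule follows shortly after the CR sentence in the same section. A coordinator who reads all of 6.9 will see it. This stands: the assessments are lost only where a site relies on the CR cross-reference or on Table 3. It does not remove the problem, because a patient-specific instruction and a schedule presented as complete both point the other way.

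It is also fair that the affected endpoints are secondary and descriptive, and that a CR already on record still counts toward best overall response. The two-stage decision is therefore not disturbed for CR stoppers.

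A reader might infer more than the documents support:

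- *That patients stopping for toxicity are also sent to survival-only follow-up.* No sentence does this. They are missing from a table, and the text covers them.
- *That a definite share of responders will be lost.* Section 1.1.2 reports 12% stopping for drug-related adverse events, which applied here gives 0.12 × 48 = 5.8 patients. That figure comes from all patients in a study of a different agent of the same class. It says nothing about responders here, and those patients are not misrouted. Adding a guessed number of CRs would give a percentage without a source.
- *That PFS will be biased in a known direction.* Section 8 names Kaplan-Meier but gives no censoring rule. Selective loss among complete responders is a reasonable worry, but neither its direction nor its size can be derived.

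**Conclusion.** The inconsistency is real and is in the current text. The CR sentence in 6.9 and the imaging row of Table 3 do not agree with 3.1.1 and the later paragraph of 6.9. The consequence is conditional: PFS, response duration and durable response at 6 and 12 months may go unobserved where a site follows the CR sentence or the table.

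For each such patient the gap is 8 to 20 weeks before month 6 and 34 to 46 weeks before month 12, given stopping at a Table 3 scan and landmarks counted from first pembrolizumab. The number of patients cannot be estimated reliably. For those who stop for toxicity or other reasons without progression, the fault is limited to the missing Table 3 entry. The primary endpoint keeps any response already recorded. A first response arising after a non-CR stop could be missed if scans lapse, but the documents do not allow that to be sized.

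This should be corrected as an inconsistency affecting secondary endpoints. It does not threaten the main conclusion of the trial.

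**What to change.** Bring the CR sentence and the table into line with the disease-assessment schedule already stated in 3.1.1 and later in 6.9:

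- In the CR sentence of 6.9, replace the pointer to 6.3.1.1 so that, after the safety visit, these patients stay in 9-weekly (± 14 days) disease follow-up. They move to 6.3.1.1 on progression or a new anticancer therapy.
- Add a Table 3 column, or a footnote to the imaging row, for patients off treatment without progression, showing imaging every 9 weeks ± 14 days.
- Extend footnote b so that its deferral of survival follow-up also applies to these patients.
- Reconcile 3.4 (stopping at CR required) with 6.9 (stopping optional). This review takes no position on which is right.

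The cost is amendment wording and one table column or footnote. It adds no scans beyond those 3.1.1 already requires.

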## **7 ADVERSE EVENTS**

### **7.1 Evaluating Adverse Events**

An investigator who is a qualified physician will evaluate all adverse events according to the NCI Common Terminology for Adverse Events (CTCAE), version 4.0. Any adverse event which changes CTCAE grade over the course of a given episode will have each change of grade recorded on the adverse event case report forms/worksheets.

All adverse events regardless of CTCAE grade must also be evaluated for seriousness.

### **7.2 Assessing and Recording Adverse Events**

An adverse event is defined as any untoward medical occurrence in a patient or clinical investigation subject administered a pharmaceutical product and which does not necessarily have to have a causal relationship with this treatment. An adverse event can therefore be any unfavorable and unintended sign (including an abnormal laboratory finding, for example), symptom, or disease temporally associated with the use of a medicinal product or protocol-specified procedure, whether or not considered related to the medicinal product or protocol-specified procedure. Any worsening (i.e., any clinically significant adverse change in frequency

and/or intensity) of a preexisting condition that is temporally associated with the use of the Merck's product, is also an adverse event.

Changes resulting from normal growth and development that do not vary significantly in frequency or severity from expected levels are not to be considered adverse events. Examples of this may include, but are not limited to, teething, typical crying in infants and children and onset of menses or menopause occurring at a physiologically appropriate time.

Merck product includes any pharmaceutical product, biological product, device, diagnostic agent or protocol-specified procedure, whether investigational (including placebo or active comparator medication) or marketed, manufactured by, licensed by, provided by or distributed by Merck for human use.

Adverse events may occur during the course of the use of Merck product in clinical trials, or as prescribed in clinical practice, from overdose (whether accidental or intentional), from abuse and from withdrawal. Progression of the cancer under study is not considered an adverse event.

All adverse events that occur after the consent form is signed but before treatment must be reported by the investigator if they cause the subject to be excluded from the trial, or are the result of a protocol-specified intervention, including but not limited to washout or discontinuation of usual therapy, diet, placebo treatment or a procedure.

From the time of treatment through 30 days following cessation of treatment, all adverse events must be reported by the investigator. Such events will be recorded at each examination on the Adverse Event case report forms/worksheets. The reporting timeframe for adverse events meeting any serious criteria is described in section 7.5.1. The investigator will make every attempt to follow all subjects with non-serious adverse events for outcome.

Adverse events will not be collected for subjects during the pre-screening period (for determination of archival tissue status) as long as that subject has not undergone any protocol-specified procedure or intervention. If the subject requires a blood draw, fresh tumor biopsy etc., the subject is first required to provide consent to the main study and AEs will be captured according to guidelines for standard AE reporting.

